### **7.9.2 Laboratory procedures**

In order to assist the identification of pathology and confirm physical health and eligibility for inclusion in the study the following blood tests will be performed: biochemistry (urea, sodium, potassium, glucose, calcium, thyroid stimulating hormone) haematology (haemoglobin, white cell count, platelets, mean red cell volume); liver function (Bilirubin, ALT, AST, Total Protein, Alkaline Phos, Albumin, Globulin, Gamma-GT). The following liver function tests will be used to assess eligibility: bilirubin, ALT, AST. The following urine drug screen will be performed [extended panel: methamphetamine, cocaine, THC, benzodiazepines, tricyclic antidepressants, barbituates, phencyclidine,, amphetamines, morphine, methadone] (urine test cup/dip test). An additional urine drug screen test for ketamine will be done on the screening visit and on visits 2, 4, 6, 8, 9 and 10. Urine pregnancy tests (urine test) will be done on the screening visit and on infusion visits.

The laboratory results will be reviewed and reports signed by the Investigator who will record in the CRF whether they are normal, abnormal but not clinically significant or abnormal AND clinically significant. In the latter case the eligibility of participants will be reviewed.

The following samples will be processed at Local Labs for screening:

- Biochemistry (urea, sodium, potassium, glucose, calcium, thyroid stimulating hormone)
- Haematology (haemoglobin, white cell count, platelets, mean red cell volume);
- Liver function (Bilirubin, ALT, AST, Total Protein, Alkaline Phos (ALP), Albumin, Globulin, Gamma-GT)

The following urine tests will be performed at site using provided kits with results recorded in the medical notes/source data (urine test cup/ dip stick test) at screening visit and on Visits 2, 4 and 6:

- Urine Drug Screen (extended panel: methamphetamine, cocaine, THC, benzodiazepines, tricyclic antidepressants, barbituates, phencyclidine, ketamine, amphetamines, morphine, methadone) (urine test cup/dip test)
- Pregnancy test (urine test)

The following urine drug screens will be performed at site using provided kits with results recorded in the medical notes/source data (urine test cup/dip stick test) at Visits 3, 5 and 7:

- Urine Drug Screen (extended panel: methamphetamine, cocaine, THC, benzodiazepines, tricyclic antidepressants, barbiturates, phencyclidine, amphetamines, morphine, methadone) (urine test cup)

The following urine drug screens will be performed at site using provided kits with results recorded in the medical notes/source data (urine test cup/dip stick test) at Visits 8, 9 and 10:

- Urine Drug Screen (extended panel: methamphetamine, cocaine, THC, benzodiazepines, tricyclic antidepressants, barbiturates, phencyclidine, ketamine, amphetamines, morphine, methadone) (urine test cup)

The following samples will be processed and analysed at local labs for all subsequent follow up visits:

- Liver function (Bilirubin, ALT, AST, Total Protein, Alkaline Phos (ALP), Albumin, Globulin, Gamma-GT)

The following samples will be processed and analysed for subsequent visits according to the study specific SOP at an HTA licensed, accredited Central Laboratory:

- BDNF
- Ketamine,

The Laboratory SOP provides the details on sample handling, processing, storage and shipment for those samples going to the central laboratory. On infusion days (visits 2, 4 and 6) blood samples will be taken to pre- and post-infusion to assess changes in BDNF and ketamine levels. Blood samples taken after the infusion will be collected after the participant has recovered from the infusion.

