### **5.2 Exclusion criteria**

1. Currently taking any other relapse prevention medication or anti-depressants
2. Current uncontrolled hypertension, systolic 140mm Hg or greater and diastolic 90mm Hg or greater
3. Currently has BMI outside normal limits <16 or > 35
4. Any relevant mental or physical health issues as determined by medically qualified personnel, which may include:
  - a. Current or history of psychosis as identified by DSM-5 or DSM-IV SCID
  - b. Current or historical diagnosis of schizophrenia in a first degree relative

- c. Co-morbid current psychiatric diagnosis excluding depression and anxiety.
  - d. Previous or current diagnosis of a substance dependence / severe substance misuse disorder as confirmed by the participant's GP or if the participant has sought professional help for their dependence
  - e. Clinically relevant history of neuropsychological difficulties
  - f. One or more previous medically confirmed seizures including seizures witnessed by an appropriate clinician, documented evidence from an EEG or a history consistent with a diagnosis of an epileptiform illness
  - g. Current suicidal ideation, as judged clinically
5. Any medication deemed, by the trial medical professionals, to pose risk combined with ketamine which may include daily prescribed use of:
- a. Barbiturates and/or narcotics
  - b. Atracurium and tubocurarine
  - c. Central nervous system (CNS) depressants (e.g. phenothiazines, sedating H1 – blockers or skeletal muscle relaxants)
  - d. Thiopental
  - e. Thyroid hormones
  - f. Antihypertensive agents
  - g. Theophylline and methylxanthine
6. Liver function tests that assess chronic liver damage (namely bilirubin, ALT, AST) > 3 times normal levels
7. Where there are "Special warnings and precautions for use" according to the SPC and where risk vs benefit ratio is not in favour of giving ketamine, with assessment made by physical examination by medically qualified trial personnel, self-report or inspection of the medical notes. Current diagnosis of:
- a. Acute intermittent porphyria
  - b. Dehydration or hypovolemia
  - c. Hyperthyroidism
  - d. Pulmonary or upper respiratory tract infection
  - e. Severe Coronary artery disease, Cerebrovascular accident or cerebral trauma
  - f. Known glaucoma or globe injuries

- g. Cirrhosis
  - h. Epilepsy
  - i. Intracranial mass lesions, hydrocephalus, or presence of head injury (i.e. evidence of lasting impact of head injury that is affecting everyday functioning)

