### **7.11.1 Discontinuation from treatment**

The investigator may discontinue a patient from treatment if it is considered necessary for any reason including:

- Ineligibility (either arising during the study or retrospective)
- Significant protocol deviation e.g. if treatment is stopped for longer than 21 days (All protocol deviations and violations will be recorded and reported to the sponsor)
- Significant non-compliance with treatment or study requirements e.g. If the participant misses 2 consecutive infusions, as detailed in section 9.12
- An adverse event which requires discontinuation of the study medication or results in inability to continue to comply with study procedures
- Disease progression which requires discontinuation of the study medication
- Pregnancy
- In the case of an overdose (see section 10.5.5)

Where treatment is discontinued, participants will be invited to attend follow up visits 9 & 10 on the basis of our planned intention to treat analysis which assumes (and formally tests: see section 13.3.4) that data are missing at random.

The reason for participant treatment discontinuation will be recorded in the case report form (CRF).

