### 10.2 Recording adverse events

All adverse events will be recorded in the medical records and CRF only following consent.

If the investigator suspects that the subjects' disease has progressed faster due to the administration of the IMP, then he will record and report

this as an unexpected adverse event. Adverse events that are known to the IMP when used in its licensed indication (listed in Appendix C, or events that are disease related or related to procedures as listed in section 10.3.3) will only be recorded in the medical notes, however serious AEs will be recorded in the CRF and SAE log.

Clinically significant abnormalities in the results of objective tests (e.g. liver function, biochemistry) will also be recorded as adverse events. If the results are not expected as part of disease or IMP, these will also be recorded as unexpected. All adverse events will be recorded with clinical symptoms and accompanied with a simple, brief description of the event, including dates as appropriate. All adverse events will be recorded until 6 months post-treatment. All Serious Adverse Events will be reportable to the Sponsor from IMP administration up to 30 days post last IMP administration.

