### **11.2 Data collection tools and source document identification**

Data to be collected can be found in sections 7.5 and 7.7. Every effort will be made to maximise completeness of data. Trial data will be collected in an Electronic Case Report Form hosted on sealedenvelope.com, prepared using their “Red Pill” service ([www.sealedenvelope.com/redpill](http://www.sealedenvelope.com/redpill)). Source data documents will be defined at site prior to the start of the trial.

Full details of source data and documentation will be identified in a separate source document identification list but in summary will comprise of the following:

- Patient Clinical Record (medical notes)
- Trial specific source data worksheets and trial specific logs

- Laboratory test print outs
- Questionnaires and measurement scales
- Encrypted memory stick containing computer tasks data files and SCRAM-X data

Data to be recorded in the source data first and then transcribed into the CRF:

- Patient demographics; age, date of birth and initials
- Medical history including drug use, alcohol use, smoking
- Physical examination
- Patient eligibility assessment
- Allergies
- Concomitant medication
- Study IMP treatment
- Therapies: Psychoeducation Therapy, Relapse-prevention based CBT
- Clinical Assessment measurements: Vital signs, Blood and urine screen. On infusion visits (visits 2, 4 and 6) continuous monitoring of vital signs will occur through the infusion until the participant has recovered. This monitoring will be recorded on a standard observation chart and will be stored as source data. The eCRF will record 3 sets of readings, one prior to the infusion, another after the infusion terminates, and then finally after the participants recovery.
- Adverse Events (refer to section 10)
- Assessment tools:
  - Pattern Recognition Test
  - Stop Signal Reaction Time
  - Delay Discounting (monetary choice questionnaire)
  - Working Memory (digit span WAIS-IV)
  - Prose Recall
  - SCRAM-X checks
  - BPRS
  - PSI
  - Adverse events VAS
  - Craving VAS
  - Fagerstrom smoking
  - Timeline follow Back
  - Drink diary
  - Reasons for drinking questionnaire
  - Columbia Suicide Severity Rating Scale
  - BDI
  - HAM-D
  - POMS

- STAI
- SF-12
- ACQ-NOW

The following data to be collected in the source documents but will not be collected in the CRF:

- Adverse events that are expected for the IMP and which are not serious and listed in section 10

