## Appendix C: Known Adverse Effects of Ketamine when used in an anaesthetic setting

The following Adverse Events have been reported:

MedDRA System Organ Class	Frequency†	Undesirable Effects
Immune system disorders	Rare	Anaphylactic reaction*
Metabolism and nutrition disorders	Uncommon	Anorexia
Psychiatric disorders	Common	Hallucination, Abnormal dreams, Nightmare, Confusion, Agitation, Abnormal behaviour
	Uncommon	Anxiety
	Rare	Delirium* Flashback*, Dysphoria*, Insomnia, Disorientation*
Nervous system disorders	Common	Nystagmus, Hypertonia, Tonic clonic movements
Eye disorders	Common	Diplopia
	Not Known	Intraocular pressure increased
Cardiac disorders	Common	Blood pressure increased, Heart rate increased
	Uncommon	Bradycardia, Arrhythmia
Vascular disorders	Uncommon	Hypotension
Respiratory, thoracic and mediastinal disorders	Common	Respiratory rate increased
	Uncommon	Respiratory depression, Laryngospasm
	Rare	Obstructive airway disorder*, Apnoea*
Gastrointestinal disorders	Common	Nausea, Vomiting
	Rare	Salivary hypersecretion*
Hepatobiliary disorders	Not known	Liver function test abnormal, Drug-induced liver injury**

Skin and subcutaneous tissue disorders	Common	Erythema, Rash morbilliform
Renal and urinary disorders	Rare	Cystitis*, Haemorrhagic cystitis*
General disorders and administration site conditions	Uncommon	Injection site pain, Injection site rash

† Common ( $\geq 1/100$  to  $< 1/10$ ); Uncommon ( $\geq 1/1,000$  to  $< 1/100$ ); Rare ( $\geq 1/10,000$  to  $< 1/1,000$ ); Not known (frequency cannot be estimated from the available data)

\* AE frequency estimated from post-marketing safety database

\*\* Extended period use (>3 days) or drug abuse

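### Post-infusion liver results need not be read before infusions 2 and 3, and the recording rules can keep a non-serious liver abnormality out of the adverse-event data

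*Protocol*

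**What the plan says.** On timing:

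- Protocol Appendix B (note d) includes liver function in the study bloods at visits 2 to 10. Visits 3 and 5 follow infusions 1 and 2. Section 7.9.2 has these tests run locally.
- Section 7.9.2 requires review: "The laboratory results will be reviewed and reports signed by the Investigator who will record in the CRF" one of three grades. For the highest grade, abnormal and clinically significant, it adds: "In the latter case the eligibility of participants will be reviewed". It gives no deadline.
- Section 5.2 excludes at entry: "Liver function tests that assess chronic liver damage (namely bilirubin, ALT, AST) > 3 times normal levels". Appendix B schedules no eligibility determination after visit 2, and the visit 4 and 6 lists in 7.7 contain no check of liver results.
- Section 7.11.1 allows, but does not oblige, the investigator to stop treatment for ineligibility that arises during the study or for an adverse event.

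On recording and reporting:

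- Section 10.2 states: "Clinically significant abnormalities in the results of objective tests (e.g. liver function, biochemistry) will also be recorded as adverse events". The same section says that effects already known for ketamine and listed in Appendix C "will only be recorded in the medical notes" unless serious. Appendix C includes "Liver function test abnormal".
- Section 11.2 keeps out of the CRF: "Adverse events that are expected for the IMP and which are not serious and listed in section 10". It also has blood results transcribed into the CRF.
- SAP 6.6 sets out adverse events descriptively by arm. SAP Tables 2, 7 and 8 contain no liver values.

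**The concern.** Safety is a primary objective, and 2.5 gives the frequency of the liver risk as unknown. Section 2.4 justifies the 3-times limit by ketamine's dependence on hepatic clearance. That reason applies to every infusion, yet the limit is written for entry only. As the text stands, infusion 2 or 3 can be given while the result from the preceding post-infusion visit is unread, even if a value exceeds the limit that would have barred the patient at entry. By contrast, the protocol does write an explicit pre-dose check for alcohol: 7.9.1 ends the visit if the breathalyser is not zero.

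On recording, two rules in one section point in different directions for the same event. If a site follows the notes-only rule, a non-serious liver abnormality does not enter the by-arm adverse-event data. The two sites could then differ in good faith.

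**Working it through.** There is no planned figure to reproduce. The check has three parts.

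**1. Do the visit windows guarantee a result before the next infusion?** Inputs from 7.7: visit 3 falls 1 to 5 days after visit 2, and visit 4 falls 4 to 21 days after visit 2.

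- Whole-day pairs: 5 × 18 = 90. One pair (visit 3 on day 5, visit 4 on day 4) reverses the visit order, leaving 89.
- Gap of 0 days: (4,4) and (5,5), so 2 pairs.
- Gap of at most 1 day: add (3,4), (4,5) and (5,6), so 5 pairs.
- Gap of at most 2 days: add (2,4), (3,5), (4,6) and (5,7), so 9 pairs.
- Stated weekly regimen, visit 4 on day 7: 7 − 5 = 2 to 7 − 1 = 6 days.
- Room to wait after the latest visit 3: 21 − 5 = 16 days.

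Visits 5 and 6 have the same windows. The windows alone do not guarantee a result in time, but they fail only at their short end. These are counts of permitted schedules, not probabilities. The absence of an instruction to read the result first applies whatever the gap.

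**2. Which recording rule governs?**

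- Section 10.2 opens with a default that adverse events go in both the medical records and the CRF.
- It then restricts non-serious Appendix C effects to the medical notes.
- It then makes clinically significant liver abnormalities adverse events, and adds that those not expected from the disease or the drug are also to be recorded as unexpected. That addition implies that expected ones are adverse events too.
- Section 11.2 excludes events listed in section 10. The list in 10.3.3 has no liver item; the liver term is in Appendix C, reached through 10.2.

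The sequence favours recording the abnormality as an adverse event, but 10.2 does not rank its rules. An event can be an adverse event and still, on the literal text, go to the notes only.

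**3. What would a withheld infusion do to the analysis?** SAP 4.5 requires three infusions for a ketamine participant to be per protocol and counts every placebo participant as per protocol. Take the planning rates (25% and 50%) with 24 per drug arm after the planned 50% drop-out: 6/24 against 12/24, relative risk 0.25/0.50 = 0.50. Remove one ketamine participant:

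- if relapsed: (5/23)/(12/24) = 0.217/0.50 = 0.43
- if not relapsed: (6/23)/(12/24) = 0.261/0.50 = 0.52

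**The case against.** The other side has a good case. Review, signature, grading and an eligibility review are all required, and 7.11.1 allows treatment to stop, so it would be wrong to infer that liver results are ignored or cannot halt dosing. The tests are local and the regimen is weekly, so results would usually be available. Section 2.5 says liver damage is not expected, and 2.4 links abnormal tests mainly to extended use or abuse, whereas this trial gives three isolated doses. On recording, the natural reading of 10.2 favours the specific liver sentence, and the grade reaches the CRF through 7.9.2 whichever rule is followed. A reader might infer that liver findings are lost from the trial data; the documents do not support that.

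It is also fair that the 3-times limit was written for entry and makes a blunt on-treatment trigger. A change from 2.9 to 3.1 times normal crosses it, and a rise from 0.8 to 2.8 does not. Any trigger should therefore refer to the participant's own baseline and keep the investigator's judgement of clinical significance. Values at visits 9 and 10 may reflect drinking, so they should not be pooled with treatment-phase values.

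What remains is that no sentence requires the result to be read before the next dose, and no sentence says that the liver rule overrides the notes-only rule.

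**Conclusion.** The point holds as a minor safety and reporting improvement. Review is required but not tied to infusion 2 or 3. Read literally, the notes-only rule can remove a non-serious liver abnormality from the adverse-event data reported by arm, though not from the CRF laboratory record.

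No effect on patients can be sized. The documents give no on-treatment incidence, and none is assumed. One could multiply out that the sign-off would cover 2 × 96 = 192 infusions, but that is the number of doses governed, not the number at risk. Likewise, 5 of 89 does not estimate how often a result would be late. A reader might also infer that patients are being harmed or that the sites do handle results differently; the documents show neither. The primary analysis is not in question.

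The conclusion rests on the protocol and SAP text alone. The Laboratory SOP is not available; 7.9.2 describes it as covering samples sent to the central laboratory, whereas the liver tests are local.

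**What to change.** 1. In 7.9.2 and Appendix B, state that infusions 2 and 3 are given only after the blinded investigator has reviewed and signed the most recent post-infusion bilirubin, ALT and AST (or the latest available results if visit 3 or 5 was missed). A clinically significant result, or a value above 3 times normal that is also higher than the participant's visit 2 value, triggers the existing eligibility review. The decision to give, delay or withhold is documented before dosing, in all four arms.
2. In 10.2 and 11.2, state that clinically significant liver abnormalities are entered in the CRF as adverse events even when listed in Appendix C.
3. Optionally, add one SAP table by arm of participants with values above 3 times normal, showing baseline, with visits 3 to 8 separate from visits 9 and 10, and the number of infusions withheld for this reason.

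No extra visit or draw is needed. The 13 samples stated in 2.5 match 1 at screening + 9 at visits 2 to 10 + 3 post-infusion, so these panels are already included.

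The cost is an occasional delayed or withheld infusion. A withheld one removes a ketamine participant, but never a placebo participant, from the per protocol set, with the shift to 0.43 or 0.52 shown above, so withheld infusions should be reported beside that analysis. Intention-to-treat membership is unchanged, provided the text says that withholding an infusion is a treatment decision and not a finding of ineligibility. Otherwise SAP 4.7, which drops participants found ineligible after randomisation from all analyses, could be applied to them.

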## **7.10 Definition of end of trial**

The end of the trial will be the last follow-up visit of the participant at 23 to 25 weeks post visit 2.

## **7.11 Discontinuation/withdrawal of participants and ‘stopping rules’**

All efforts will be made to maintain participants in the study where possible and to continue assessments as intended. However, there are circumstances under which treatment may be discontinued and/or participants withdrawn from the trial.

### **7.11.1 Discontinuation from treatment**

The investigator may discontinue a patient from treatment if it is considered necessary for any reason including:

- Ineligibility (either arising during the study or retrospective)
- Significant protocol deviation e.g. if treatment is stopped for longer than 21 days (All protocol deviations and violations will be recorded and reported to the sponsor)
- Significant non-compliance with treatment or study requirements e.g. If the participant misses 2 consecutive infusions, as detailed in section 9.12
- An adverse event which requires discontinuation of the study medication or results in inability to continue to comply with study procedures
- Disease progression which requires discontinuation of the study medication
- Pregnancy
- In the case of an overdose (see section 10.5.5)

Where treatment is discontinued, participants will be invited to attend follow up visits 9 & 10 on the basis of our planned intention to treat analysis which assumes (and formally tests: see section 13.3.4) that data are missing at random.

The reason for participant treatment discontinuation will be recorded in the case report form (CRF).

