### **13.3.4 Sensitivity and other planned analyses**

All participants will be in a state of detoxification at recruitment, hence in the event of loss to follow-up, it is not appropriate to make an assumption that the participant had or had not relapsed at 6 months. To address the issue of missing data due to loss to follow-up, a sensitivity analysis will be performed using multiple imputation methods, for relapse at 6-month follow-up only, making the assumption that all missing data were missing at random.

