4.5 Purpose of the analyses

The purposes of the analyses are as follows:

- (i) to provide baseline descriptive data by trial arm;
- (ii) to assess the feasibility of data collection;
- (iii) to assess loss to follow-up at 3 and 6 months;

- (iv) to assess the proportion of missing data at 6 months;
- (v) to provide descriptive outcome data by trial arm (ketamine vs placebo, psychotherapy vs psychoeducation, and all four arms individually) at 6 months;
- (vi) to provide relative risks (with 95% confidence intervals) for relapse of alcohol consumption comparing (a) ketamine vs placebo; (b) ketamine plus psychotherapy vs ketamine plus psychoeducation; (c) ketamine plus psychotherapy vs placebo plus psychoeducation;
- (vii) to provide mean difference (with 95% confidence intervals) for percentage of days abstinent at 6-month follow-up for the same combinations by arm as for (vi); and
- (viii) to descriptively report adverse events.

All inferential analyses are to be regarded as exploratory and viewed with caution due to lack of statistical power and multiple testing. For the primary outcomes, the primary analyses will be performed on an intention to treat (ITT) basis using complete case data only (see Section 6.5 for approaches to missing primary outcome data). As a sensitivity analysis, the inferential analyses for the primary outcomes only (vi and vii above) will be performed using only those participants deemed to have completed their allocated interventions to a specified degree (per protocol analysis). For the participants who receive ketamine, a per protocol treatment will be defined as receiving three or more infusions. No specification of a minimum treatment has been defined for psychotherapy/psychoeducation. Hence, all participants who receive placebo drug therapy will be considered as having been treated per protocol. For the secondary outcomes, only an ITT analysis using complete case data will be performed. All analyses will be performed by a statistician who is blinded to treatment allocation. All analyses will be performed using Stata v14.

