4.7 Study populations

Inclusion and exclusion criteria for participants are set out in the Protocol, Final Version 12, 20.01.2020 Section 5.

The primary analyses will be performed using the ITT population (participants analysed according to their randomised allocations). Further sensitivity analyses will be performed using the per protocol population (defined in Section 4.5). All analyses will be performed using complete case data only. Participants found to be ineligible after randomisation will be excluded from all analyses.

5. Study objectives and endpoints

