6.5 Missing data

The primary analyses for primary and secondary outcomes will be based on complete case data only. For the primary outcomes only, we will use multiple imputation to impute any missing data, if data are missing for more than 5% of participants. Individual item missingness for questionnaire outcomes will be dealt with by using the average of reported items to substitute for missing items if no more than a certain number (to be determined for each questionnaire) of items are missing.

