Table 5 Relapse of alcohol use and percentage of days abstinent at 6-month follow-up: per protocol^a population using complete case data.

Outcome	Ketamine (n=)	Placebo (n=)	PT (n=)	PE (n=)	Ketamine + PT (n)	Ketamine + PE (n)	Placebo + PT (n)	Placebo + PE (n)	Ketamine vs placebo RR (95% CI)	Ketamine + PT vs Ketamine + PE RR (95% CI)	Ketamine + PT vs placebo +PE RR (95% CI)
Relapse; n (%) Timeline follow back											
									Ketamine vs placebo mean difference (95% CI)	Ketamine + PT vs Ketamine + PE mean difference (95% CI)	Ketamine + PT vs placebo +PE mean difference (95% CI)
Percentage days abstinent; mean (SD); median [IQR] Timeline follow back											

^aPer protocol population defined as receiving at least three ketamine infusions. No definition of per protocol for placebo, psychotherapy, or psychoeducation interventions.

PE: Psychoeducation

PT: Psychotherapy

Table 6 Relapse of alcohol use and percentage of days abstinent at 6-month follow-up: intention to treat population using complete case and imputed data.

Outcome	Ketamine (n=)	Placebo (n=)	PT (n=)	PE (n=)	Ketamine + PT (n)	Ketamine + PE (n)	Placebo + PT (n)	Placebo + PE (n)	Ketamine vs placebo RR (95% CI)	Ketamine + PT vs Ketamine + PE RR (95% CI)	Ketamine + PT vs placebo +PE RR (95% CI)
Relapse; n (%) Timeline follow back											
									Ketamine vs placebo mean difference (95% CI)	Ketamine + PT vs Ketamine + PE mean difference (95% CI)	Ketamine + PT vs placebo +PE mean difference (95% CI)
Percentage days abstinent; mean (SD); median [IQR] Timeline follow back											

PE: Psychoeducation

PT: Psychotherapy

Table 7 Secondary outcomes at 3-month follow-up

Outcome	Ketamine (n=)	Placebo (n=)	PT (n=)	PE (n=)	Ketamine + PT (n)	Ketamine + PE (n)	Placebo + PT (n)	Placebo + PE (n)	Ketamine vs placebo mean difference (95% CI)
Number of continuous days abstinent ^{a,b} ; mean (SD), median [IQR]									
Percentage days abstinent ^{a,b} ; mean (SD); median [IQR]									

PE: Psychoeducation

PT: Psychotherapy

^aAbstinent means not using alcohol at all.

^bOutcomes measured using timeline follow-back.

Table 8 Secondary outcomes at 6-month follow-up

Outcome	Ketamine (n=)	Placebo (n=)	PT (n=)	PE (n=)	Ketamine + PT (n)	Ketamine + PE (n)	Placebo + PT (n)	Placebo + PE (n)	Ketamine vs placebo mean difference (95% CI)
Profile of Mood states; mean (SD), n									
Beck Depression Inventory; mean (SD)									
Hamilton Depression Scale; mean (SD), n									

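### Protocol 7.11.1 claims a formal test of missing at random that neither document contains, and complete-case analysis, the only one planned for 17 six-month secondary variables, needs a stronger condition than that

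*Protocol*

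**What the plan says.** Protocol 7.11.1 explains why participants who stop treatment are still invited to visits 9 and 10: it is for the "planned intention to treat analysis which assumes (and formally tests: see section 13.3.4) that data are missing at random". The section it points to, Protocol 13.3.4, plans multiple imputation, "making the assumption that all missing data were missing at random". It describes no test.

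The analyses themselves are set out as follows.

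- **Primary outcomes.** Protocol 13.3.2 and SAP 4.5, 6.2 and 6.5 make the ITT complete-case analysis primary. SAP 6.3 adjusts for site and nothing else.
- **Secondary outcomes.** SAP 4.5: "For the secondary outcomes, only an ITT analysis using complete case data will be performed".
- **Imputation in the protocol.** Section 13.3.4: "a sensitivity analysis will be performed using multiple imputation methods, for relapse at 6-month follow-up only". The Protocol Summary has the same restriction.
- **Imputation in the SAP.** Section 6.5: "For the primary outcomes only, we will use multiple imputation to impute any missing data, if data are missing for more than 5% of participants". The title of SAP Table 6 promises an "intention to treat population using complete case and imputed data", with rows for relapse and for percentage days abstinent.
- **General rule in the SAP.** Section 4.7: "All analyses will be performed using complete case data only".

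**The concern.** There are three linked problems.

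First, the protocol states that an assumption is tested when it is only assumed. No test could settle the matter, because the observed data do not distinguish MAR from missing not at random. A report that relied on 7.11.1 would claim a check that nobody made.

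Second, the stated assumption and the main analysis do not match. MAR allows loss to depend on anything already observed, including earlier scores. A complete-case comparison at 6 months adjusted for site is unbiased only if loss is unrelated to the outcome given arm and site. Outcome-related loss is plausible on the protocol's own terms. Section 7.9.1 ends any visit, including visits 9 and 10, when the breathalyser is not zero, with re-attendance only inside the window. Section 7.11.2 lists disease progression and failure to respond among the reasons for withdrawal. Section 2.4 says depressive symptoms are thought to precipitate relapse.

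Third, the secondary scales have no other analysis. Someone with scores at visits 8 and 9 but not at visit 10 contributes nothing to the 6-month comparison in SAP Table 8.

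At stake are the point estimates and 95% confidence intervals, which are what the trial will report (SAP 6.4).

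**Working it through.** **1. The plan's own figures.** Half of 96 leaves 48, or 24 per drug arm. The 90% interval for a fall from 50% to 25% is 0.25 ± 1.645 × √(0.5×0.5/24 + 0.25×0.75/24) = 0.25 ± 1.645 × 0.135 = 0.028 to 0.472, which matches the protocol's 3% to 47%. The SAP's 37-point width matches the exact 95% interval for 6/24 (9.8% to 46.7%, width 36.9). Both figures describe precision at 50% loss and are silent on bias.

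**2. Counting the variables.** SAP 5.2 lists 19 secondary variables. Removing the two 3-month abstinence variables leaves 17. Protocol Appendix B schedules all 17 at baseline and at visits 8, 9 and 10, and most at visits in between as well.

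**3. Relapse, with loss depending on relapse by month 3.** Let p be the true 6-month relapse rate, s the share of relapses that occur by month 3, and d1 and d0 the later loss among those relapsed and not relapsed by month 3. Then

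complete-case rate = [sp(1−d1) + (1−s)p(1−d0)] / [sp(1−d1) + (1−sp)(1−d0)].

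From the documents: p = 50% and 25%, and 50% overall loss. Assumed: s = 0.7 and the odds ratio (OR) linking d1 to d0, the same in both arms. At OR 4, d0 = 0.41 and d1 = 0.74. For placebo the numerator is 0.35×0.26 + 0.15×0.59 = 0.1795 and the denominator is 0.35×0.26 + 0.65×0.59 = 0.4745, giving 0.38.

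| OR | Placebo | Ketamine | RR | Difference |
|---|---|---|---|---|
| 1 | 50% | 25% | 0.50 | 25 points |
| 2 | 44% | 21% | 0.47 | 23 points |
| 4 | 38% | 17% | 0.45 | 21 points |
| 8 | 33% | 14% | 0.43 | 19 points |

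With s from 0.5 to 0.9 and OR 2 to 8, the RR runs from 0.48 to 0.41. At 20% loss and OR 4 (s = 0.7) it is 0.47. If the dependence exists in one arm only (OR 4, 50% loss in each arm), the RR is 0.65 when that arm is placebo and 0.33 when it is ketamine. In simulation, an estimator using the 3-month data returned about 50% and 25% in every common-mechanism case.

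**4. Percentage days abstinent.** Assumed: true difference 15 points, SD 30, correlation between months 3 and 6 of 0.5 to 0.8, 50% loss (48 per arm, 4,000 runs). Complete-case gives 14.1 down to 10.3 points under a common mechanism, from weak to strong dependence, and 6.4 to 1.1 if loss depends on 3-month drinking in placebo only. A model using the 3-month value gives about 15 throughout.

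**5. The scales.** Assumed: true effect 0.50 SD and loss depending on the last observed score in the same way in both arms.

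- *Loss only after visit 8* (48 per arm, about 50% completers, 3,000 runs): at correlations 0.5, 0.6, 0.7 and 0.8 complete-case gives 0.44, 0.43, 0.42 and 0.42 SD. Doubling the dependence at 0.7 gives 0.33. A likelihood model on visits 8, 9 and 10 gives about 0.50 throughout, with a standard error 1% to 11% smaller.
- *Some loss before visit 8* (correlation 0.7, 51% to 56% completers): complete-case gives 0.33 to 0.42 SD. A model on visits 8 to 10 alone gives only 0.38 to 0.46. A model that also uses baseline and the earlier visits gives 0.49 to 0.50, with an equal or smaller standard error.
- *Loss unrelated to scores:* complete-case and the visits 8 to 10 model are both unbiased, and the model's standard error is 6% to 16% smaller.

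**The case against.** The strongest reply is that the plan is better than this sounds. An MAR method is already planned for the primary outcomes and has its own results table. The 50% is called very conservative in Protocol 13.2.1 and is conditional in SAP 4.6. Inviting people who stop treatment to visits 9 and 10 should itself limit loss. All comparisons are declared exploratory and carry no p-values. For the scales, the shortfall of 0.08 to 0.17 SD compares with a standard error of about √(2/24) = 0.29 SD, so it is roughly 0.3 to 0.6 standard errors. The strength of dependence, the correlations and the effect size are not in the documents.

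Most of that stands, and it limits the point. A reader might infer that every planned analysis is complete-case, that half the sample is expected to be lost, or that the estimates are biased. The documents support none of these. Imputation is planned for the primary outcomes, 50% is a planning allowance, and bias arises only under some mechanisms. Nor is it always attenuation: in step 3 the RR moves away from 1 while the risk difference shrinks.

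What remains is not answered by the reply. The claim of a test is wrong as written. Imputation never reaches the 17 scales, and its model is unspecified, so nothing says earlier drinking data enter it. The exploratory label does not protect point estimates and intervals, which are the stated product.

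**Conclusion.** The point holds in this form. The formal test announced in Protocol 7.11.1 does not exist and could not do what is claimed. The main analyses of the primary outcomes, and the only analyses of 17 secondary variables, need a stronger condition than the MAR assumption the protocol adopts. SAP 4.7 contradicts SAP 6.5 and Table 6, and the two documents differ on which primary outcomes are imputed.

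Complete-case estimates can be biased if loss depends on earlier observed scores. With about half lost, correlation 0.7 and a common mechanism of assumed strength, 0.50 SD becomes about 0.33 to 0.42 SD. With less loss the bias is smaller; with loss unrelated to outcome given arm and site it is nil.

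A reader might also infer that a repeated-measures model on visits 8 to 10 would be enough. It is enough only when nobody is lost before visit 8. One limit applies to the fuller model too: in Appendix B the nicotine score, both SF-12 components, delay discounting, stop-signal time and digit span are collected only at baseline and visits 8 to 10. For these six, earlier loss can be addressed only through baseline.

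**What to change.** - **Protocol 7.11.1:** delete the parenthesis claiming a formal test, so that the sentence says only that MAR is assumed.
- **SAP 4.5, 6.2 and 6.5:** analyse the 6-month scale outcomes with a likelihood repeated-measures model that includes baseline and all post-randomisation visits at which the scale is collected, not only visits 8 to 10, with arm-by-visit and site terms. Report the visit 10 contrast and keep complete-case as the sensitivity analysis.
- **SAP 4.7, SAP 6.5 and Table 6:** reconcile the complete-case-only rule with the planned imputation.
- **Protocol 13.3.4 and Summary:** reconcile relapse-only imputation with the SAP's imputation of both primary outcomes. Specify the imputation model, with earlier timeline follow-back data as predictors.

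The cost is wording plus one standard model per scale, with no new data. The model assumes normality, which may suit some variables poorly, such as the smokers-only nicotine score and the adverse-effects VAS; those could stay complete-case.
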